STUDY PROTOCOL NCR191281

OFFICIAL TITLE:

How Will an Educational Video About the Induction of Labor Process Impact Patient's Knowledge of and Satisfaction With the Induction Process

Document Date: 8/27/2020

Recruitment and Data Collection:

Patients were screened for study enrollment during routine prenatal visits at the George Washington University Hospital. A trained research team member met with and spoke to eligible patients about the randomized study at the time of their scheduled induction of labor visit. There was an induction of labor schedule that is created monthly, which the research team members had access to and determined when eligible participants had their induction of labor visit scheduled.

Informed consent was obtained from the patient if interested in participating. Privacy and confidentiality were assured as approved team members were the only individuals with access to patient records and maintained strict confidentiality. All consent forms were kept in a locked cabinet and survey responses were de-identified. Patients were able to ask questions and/or opt out of the study at any time.

The research team member assessed patient's understanding of the information and participation by asking them to describe in their own words what they were consenting to. Signed informed consent were obtained prior to study enrollment.

Once a patient was enrolled, participants were randomized to the control group (no intervention) or the intervention group (3-minute educational video intervention). The randomization schedule was predetermined. The enrolled participant was given a pre-randomized study envelope that contained a unique Study ID number, randomization group, and paper surveys.

The control group took the knowledge-based survey. Twenty-four to forty-eight hours after delivery, at a time convenient to the participant during the postpartum stay at GW, a research team member asked the participant to fill out a second survey, focused on satisfaction with the labor and delivery process.

The intervention group had the opportunity to watch the 3-minute educational video. The video shown to these participants is linked here: <https://youtu.be/Pc9tclV4Dm8>. After watching the video, the participant was asked to take the knowledge-based survey. Twenty-four to forty-eight hours after delivery, at a time convenient to the participant during the postpartum stay at GW, a research team member asked the participant to fill out a second survey, focused on satisfaction.

If the patient ultimately chose not to participate in the study following the signing of informed consent, all their data was destroyed. All of the surveys were stored in a locked cabinet, secured. No one but the research team members had access to the collected data and none of the stored paper copies had any identifying information. The basic demographic information, as well as the outcome of the induction of labor process, was collected using the hospital's electronic medical record. Some of the information (race and ethnicity) was collected by self-report.

Recruitment goal:

At minimum, the goal was an n= of 106 total, 53 per arm. This was powered based on an alpha of 0.05, 80% power, 10% attrition rate to accurately detect a 20% difference given 96% correct in the intervention group.

Data entry:

After enrollment and completion of study surveys, a member of the research team entered in all of the information collected into a de-identified Redcap database using the unique Study ID numbers. The research team also collected data from the patient's electronic medical record about the enrolled participant's induction of labor process, including gravity, parity, pregnancy complications, induction agents utilized, and delivery method (vaginal vs cesarean delivery). All of this data was entered into the de-identified Redcap database. Access to the participant's medical record was only available to the research team through the MFA's HIPAA compliant, password protected, firewalled electronic medical record (Allscripts) and GW hospitals' EMR (Cerner).

After the data was entered into Redcap, a second and different member of the research team re-checked the entry to ensure the answers were correctly captured into the system.

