STATISTICAL ANALYSIS PLAN NCR191281

OFFICIAL TITLE:

How Will an Educational Video About the Induction of Labor Process Impact Patient's Knowledge of and Satisfaction With the Induction Process

Document Date: 8/27/2020

Statistical Analysis methods:

Methods:

Baseline knowledge score was calculated as the number of correct answers from the baseline knowledge survey questions 6 through 15 (10 questions total), presented as a percentage correct out of 100%. Satisfaction survey questions 1 through 6 were analyzed on a Likert Scale (1 being the least satisfied, 3 being neutral, 5 being the most satisfied). After utilizing Cronbach's α to identify the high level of similarity between these 6 questions in measuring satisfaction, resulting responses on the Likert Scale from questions 1 through 6 were averaged to get a distribution of overall satisfaction that would span all 6 questions of interest but result in one single score on the Likert scale (between 1 and 5) per respondent.

Baseline knowledge and satisfaction were compared between randomized intervention and control arms using the Mann-Whitney U test in order to test for significant differences in baseline knowledge and induction process satisfaction between those who received the survey with the video compared to those only received the survey. Sub-analyses analyzed baseline knowledge differences between those who had a prior induction, those who had no prior induction, those who were nulliparous, and those who were multiparous. Sub-analyses additionally investigated satisfaction with the induction process sub-stratified by those who had a cesarean delivery and those that had a history of a prior induction. All statistical analysis was performed using SAS version 9.4 (SAS Institute Inc., Cary, NC) with a two-sided p-value less than 0.05 considered statistically significant.

Results:

From October 2019 to February 2020, 145 scheduled IOLs were eligible and approached for the study. 129 participants consented, and 119 completed the entire study. 64 were randomized into the control group and 55 into the intervention group.

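### The data-destruction rule has no cut-off at randomization, so an allocated woman who opts out can lose all her data, including valid knowledge scores

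*Protocol*

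**What the plan says.** All of the relevant Protocol text is under Recruitment and Data Collection.

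- **Order of events.** "Signed informed consent were obtained prior to study enrollment". Allocation follows: "Once a patient was enrolled, participants were randomized to the control group (no intervention) or the intervention group".
- **Awareness of arm.** "The enrolled participant was given a pre-randomized study envelope that contained a unique Study ID number, randomization group, and paper surveys". Only the intervention arm is offered the video.
- **Timing of outcomes.** The knowledge survey is taken at the induction visit, after the video in the intervention arm. The satisfaction survey comes later: "Twenty-four to forty-eight hours after delivery, at a time convenient to the participant during the postpartum stay at GW".
- **Leaving the study.** "Patients were able to ask questions and/or opt out of the study at any time".
- **What happens to the data.** "If the patient ultimately chose not to participate in the study following the signing of informed consent, all their data was destroyed".

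The SAP, under Results, reports: "129 participants consented, and 119 completed the entire study". It gives the randomized numbers as 64 control and 55 intervention. Neither document gives the arm, timing or reason for the other ten women. Neither defines an intention-to-treat set or a method for missing data.

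**The concern.** The destruction rule starts at the signing of consent and has no stated end. Allocation, the knowledge survey, delivery and the satisfaction survey all fall after that point. A choice made after randomization can therefore remove a woman from the trial entirely, and by then she can know her arm and may have been through labor.

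Two things are at stake. First, a knowledge score that was complete and valid before any reason to leave arose is discarded, together with the delivery data. Second, satisfaction is self-reported after delivery, so a decision to leave could plausibly be related to the score the woman would have given. Ordinary dropout leaves earlier data that can support a sensitivity analysis. Under this rule nothing of the woman's own data remains for that purpose.

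**Working it through.** **1. Reach of the rule.** Consent comes before enrollment, and enrollment before randomization. Opting out is open throughout, and destruction applies to any choice not to participate made after consent. No sentence limits it to the interval before the envelope. The rule therefore covers randomized women.

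**2. Is power affected?** The plan's own figure reproduces. Inputs from Recruitment goal are 96% vs 76% (20 points, read as absolute), alpha 0.05 (two-sided per the SAP), 80% power and 10% attrition. With mean proportion 0.86:

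n = [1.96·√(2·0.86·0.14) + 0.8416·√(0.96·0.04 + 0.76·0.24)]² / 0.20² = (0.962 + 0.395)² / 0.04 ≈ 46.1, so 47 per arm.

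47/0.90 = 52.2, so 53 per arm and 106 in total. There were 119 completers, and the loss from consent to completion is (129 − 119)/129 = 10/129 = 7.8%, below the planned 10%. Power is not the issue.

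**3. Possible losses after randomization.** Read literally, 64 + 55 = 119 randomized equals the number of completers, so the loss after randomization could be zero. If instead all ten had been allocated:

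| Split of the ten | Intervention lost | Control lost |
|---|---|---|
| All intervention | 10/65 = 15.4% | 0/64 = 0% |
| 5 and 5 | 5/60 = 8.3% | 5/69 = 7.2% |
| All control | 0/55 = 0% | 10/74 = 13.5% |

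**4. What this could do to satisfaction.** The SAP reports medians (quartiles) of 4.3 (4.0, 4.5) for intervention and 3.6 (2.9, 4.2) for control, with p<0.001. Scores were rebuilt by linear interpolation between the minimum, the quartiles and a maximum of 5, for n = 55 and n = 64, and rounded to sixths because six items are averaged. The minima are not reported and are assumed. All sets shown keep the observed p below 0.001. Entries are two-sided Mann-Whitney p-values.

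| Assumed minimum (intervention, control) | Observed | 10 intervention at 1 | 10 intervention at 3 | 5/5 at 1 | 10 control at 1 |
|---|---|---|---|---|---|
| 3.5, 1 | 0.000002 | 0.006 | 0.0004 | 0.00004 | <0.0001 |
| 3, 1 | 0.00002 | 0.020 | 0.0016 | 0.0002 | <0.0001 |
| 2.5, 1 | 0.00007 | 0.044 | 0.0044 | 0.0006 | <0.0001 |
| 2, 1 | 0.0002 | 0.077 | 0.0095 | 0.0015 | <0.0001 |
| 2, 2 | 0.0004 | 0.108 | 0.014 | 0.0026 | <0.0001 |

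With ten intervention women added at score 1, the rebuilt intervention median is 4.17 against 3.58 for control, so the order of the medians does not reverse. In every row, ten controls at score 1 give a smaller p than the observed comparison. Controls lost with high scores would weaken the effect: ten at score 5 give about 0.003 to 0.06. That is the reverse of dissatisfied women leaving.

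**5. Knowledge.** In a similar reconstruction (medians 90% vs 60%; intervention minimum assumed 50 or 0, control minimum 20), adding ten intervention women at 0% leaves p at about 0.0006 or below.

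**The case against.** Several objections have force.

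- **The sentence may concern only early changes of mind.** Taken alone, it can be read as covering women who reconsider soon after signing. Nothing states that limit, however, and the freedom to leave is open-ended. The narrow reading is possible but not secured by the text.
- **Skipping a survey is not opting out.** A reader might infer that a woman who declines or misses the postpartum survey has all her data destroyed. The documents do not say so: both sentences concern participation in the study as a whole. This objection stands, and it shows that opt-out needs a definition.
- **Counts by arm may be recoverable.** A reader might infer that losses can never be described by arm. The rule destroys a participant's data; nothing says that it destroys the predetermined schedule or the record of numbered envelopes. What is lost for good is outcome data. This objection stands too.
- **No loss after randomization is shown.** A reader might take the 64 to 55 imbalance as a sign that intervention women were removed, since a 65:64 allocation of 129 would place all ten losses there. The documents do not support this. The ten may have left before allocation or simply missed a survey, and 55 of 119 is compatible with simple 1:1 randomization (p = 0.46).
- **The adverse p-values are a one-sided extreme.** They place all ten women in one arm at the lowest score, and they move with the assumed tails. If dissatisfaction drives leaving, low-scoring controls may leave as well, which would make the reported effect too small.
- **Accrual is over.** Recruitment ran from October 2019 to February 2020 and the document is dated 8/27/2020. New wording recovers nothing for this trial. The consent pages are not available here, so what participants were promised about deletion cannot be checked.

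**Conclusion.** The concern holds as a flaw in a stated rule. The Protocol permits outcome-related exclusion after randomization and removes the data with which it could be examined. It does not establish that any exclusion of this kind occurred.

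The size is bounded by ten women, and zero is a possible value. The reported satisfaction difference would lose its strength only if most or all of the ten were allocated and were lost in the unfavourable direction. An even split at the lowest score leaves it clearly significant. The direction of the knowledge result is not in doubt in any scenario examined. The satisfaction figures rest on interpolated data with assumed minima and should be read as bounds, not estimates. A change is warranted, but the trial's conclusions are not overturned.

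**What to change.** **For the rule, in any extension or reuse of the Protocol.** Replace the sentence with wording to this effect: a participant who opts out after randomization stops further study procedures; her allocation, date of opt-out and de-identified data already collected, including a completed knowledge survey, are kept and analysed in her assigned arm unless she asks for deletion, in which case only an anonymous count by arm is kept. Add that declining or missing the postpartum survey alone is missing data and not an opt-out.

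**For this trial.** Use the predetermined schedule and the used envelopes, where possible, to report the numbers randomized, withdrawn and analysed by arm, with timing. If any randomized woman was removed, or if the counts cannot be rebuilt, say so and qualify the satisfaction conclusion.

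**Cost.** A short wording change in the protocol and the consent form, and a few women in the dataset with knowledge but no satisfaction data. For the completed trial, the cost is a reconciliation of envelopes against the schedule.

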STATISTICAL ANALYSIS PLAN NCR191281

OFFICIAL TITLE:

How Will an Educational Video About the Induction of Labor Process Impact Patient's Knowledge of and Satisfaction With the Induction Process

Document Date: 8/27/2020

Statistical Analysis methods:

Methods:

Baseline knowledge score was calculated as the number of correct answers from the baseline knowledge survey questions 6 through 15 (10 questions total), presented as a percentage correct out of 100%. Satisfaction survey questions 1 through 6 were analyzed on a Likert Scale (1 being the least satisfied, 3 being neutral, 5 being the most satisfied). After utilizing Cronbach's α to identify the high level of similarity between these 6 questions in measuring satisfaction, resulting responses on the Likert Scale from questions 1 through 6 were averaged to get a distribution of overall satisfaction that would span all 6 questions of interest but result in one single score on the Likert scale (between 1 and 5) per respondent.

Baseline knowledge and satisfaction were compared between randomized intervention and control arms using the Mann-Whitney U test in order to test for significant differences in baseline knowledge and induction process satisfaction between those who received the survey with the video compared to those only received the survey. Sub-analyses analyzed baseline knowledge differences between those who had a prior induction, those who had no prior induction, those who were nulliparous, and those who were multiparous. Sub-analyses additionally investigated satisfaction with the induction process sub-stratified by those who had a cesarean delivery and those that had a history of a prior induction. All statistical analysis was performed using SAS version 9.4 (SAS Institute Inc., Cary, NC) with a two-sided p-value less than 0.05 considered statistically significant.

Results:

From October 2019 to February 2020, 145 scheduled IOLs were eligible and approached for the study. 129 participants consented, and 119 completed the entire study. 64 were randomized into the control group and 55 into the intervention group.

The median (quartile 1, quartile 3) baseline knowledge score for the randomized intervention cohort was 90% (90%, 100%) relative to 60% (50%, 70%) for the control cohort, indicating that the baseline knowledge scores were significantly higher for the intervention cohort (p<0.001). This same trend was seen when comparing only those who had prior induction (median 90% vs 60%, p=0.002), no prior induction (100% vs 60%, p<0.001), nulliparous women (90% vs 60%, p<0.001), and multiparous women (100% vs 60%, p<0.001).

Cronbach's α for Likert Scale satisfaction questions 1 through 6 was α =0.854, indicating ideal similar measure across questions for quantifying satisfaction. The median (quartile 1, quartile 3) overall satisfaction score for the randomized intervention cohort was 4.3 (4.0, 4.5) relative to 3.6 (2.9, 4.2) for the control cohort, indicating that satisfaction was significantly higher in those that received the intervention (p<0.001). In looking at only women who delivered via cesarean, satisfaction was still significant higher in the intervention group (median 3.9 vs 3.0, p=0.003).

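### Does calling the knowledge score 'baseline' mean the SAP reports a pre-treatment imbalance instead of an effect of the video?

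*SAP*

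**What the plan says.** The protocol (Recruitment and Data Collection) randomizes each participant on enrollment and then hands over the materials: "The enrolled participant was given a pre-randomized study envelope that contained a unique Study ID number, randomization group, and paper surveys". Of the arm without the video it says only "The control group took the knowledge-based survey". Of the other arm it says "After watching the video, the participant was asked to take the knowledge-based survey". Between 24 and 48 hours after delivery, a team member "asked the participant to fill out a second survey, focused on satisfaction with the labor and delivery process". No other survey is described. Under Recruitment goal the trial is sized on knowledge, "to accurately detect a 20% difference given 96% correct in the intervention group".

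The SAP (Methods) defines the score: "Baseline knowledge score was calculated as the number of correct answers from the baseline knowledge survey questions 6 through 15". It then compares knowledge and satisfaction between the randomized arms by the Mann-Whitney U test, to look for differences "between those who received the survey with the video compared to those only received the survey". The Results report the medians with their quartiles, conclude "indicating that the baseline knowledge scores were significantly higher for the intervention cohort (p<0.001"), and say that the same pattern held in four subgroups.

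**The concern.** To a trial reader, a baseline value is one recorded before the intervention. Taken that way, the Results sentence says that the video arm already knew more before seeing the video. That would be a failure of comparability, and it would undercut the answer to the trial's title question. The label could also suggest that a pre-video knowledge measurement exists, so that change within a participant could be studied. The protocol describes no such measurement. The word is not an isolated typing error either: it is in the score definition, the comparison, the sub-analysis plan and the conclusion.

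**Working it through.** The question is mainly one of timing and wording, so the texts are set side by side. One rough calculation follows.

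**1. When knowledge was measured (protocol, Recruitment and Data Collection).**

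| Step | Control arm | Intervention arm |
|---|---|---|
| Enrollment and randomization | yes | yes |
| Envelope with group and surveys | yes | yes |
| Video | no | yes |
| Knowledge survey | after randomization, no video | after randomization and after the video |
| Satisfaction survey | 24–48 hours after delivery | 24–48 hours after delivery |

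There is one knowledge measurement per participant, and it comes after randomization in both arms. It is an outcome.

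**2. How often the label occurs.** The word appears 5 times in the SAP's Methods and 2 times in its Results, 5 + 2 = 7, and 0 times in the protocol. In the Results both uses fall in one sentence and concern one comparison (90% vs 60%). The four subgroup results take the label only by reference back to that sentence.

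**3. Which meaning fits the rest of the text.**

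- *Measured before treatment.* This conflicts with the protocol's sequence. It also conflicts with the SAP's own description of the contrast ("between those who received the survey with the video compared to those only received the survey") and with a sample size built on percent correct in the intervention arm.
- *First survey, taken before the induction.* This fits the protocol's sequence, the protocol's description of the satisfaction questionnaire as the second survey, and the SAP's description of the contrast. The questionnaire itself is not in the documents, so whether the word is part of its title cannot be checked.

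Only the second meaning is consistent with both documents.

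**4. Could the difference be a chance imbalance?** Inputs from the SAP's Results: quartiles 50% to 70% in 64 controls and 90% to 100% in 55 intervention participants; medians 60% and 90%. Take SD ≈ interquartile range / 1.349 and treat the medians as means. Both are approximations for a bounded 10-item score.

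- Control SD ≈ 20 / 1.349 = 14.8; intervention SD ≈ 10 / 1.349 = 7.4.
- Standard error = √(14.83²/64 + 7.41²/55) = √(3.43 + 1.00) = 2.11; 30 / 2.11 ≈ 14.2 standard errors.
- With the larger SD in both arms: 14.83 × √(1/64 + 1/55) = 2.73; 30 / 2.73 ≈ 11.0 standard errors.

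A gap of 11 to 14 standard errors between randomized groups is not a chance pre-treatment difference. This does not date the survey; the protocol's sequence does that. It does show that a reader who took the label literally would at once see that something else was meant.

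**5. What relabelling would change.** The medians (90% and 60%), their quartiles, the Mann-Whitney test, p<0.001, the arm sizes (64 + 55 = 119) and the four subgroup comparisons all stay as they are.

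**The case for a change.** The best case for a change is that the label is undefined, used throughout, and placed in the sentence that reports the main knowledge result. A reader who sees only that sentence could be misled about the very question in the title, and new wording would cost almost nothing. A plain statement that no pre-video score was taken would also tell readers that prior knowledge cannot be compared between arms and that change within a participant cannot be estimated.

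Part of this stands. The term is a poor choice, and the misreading is possible from that sentence in isolation. But calling the conclusion itself wrong goes too far. On the first-survey meaning the sentence is true and badly labelled, and the SAP's Methods supply the correct contrast a short way above it. The lack of a pre-video score is plain from the protocol's sequence, and a between-arm comparison after randomization does not need one to be valid. The SAP's Methods sentence on sub-analyses is also loosely worded, as if the subgroups were compared with each other, but the Results show that each comparison is between arms within a subgroup.

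**Conclusion.** The concern identifies a real but clerical slip and does not call for a change to the plan. The SAP attaches an undefined and misleading word to a post-randomization outcome, seven times. Its Methods nevertheless state the intended comparison, and the protocol's sequence leaves no doubt about timing. The SAP is dated August 2020, describes recruitment from October 2019 to February 2020 and already reports the results, so a new label could not redirect any analysis. The effect on every estimate, test and p-value is nil.

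This rests on two assumptions: that the protocol describes every knowledge measurement taken, and that the word means the first survey. If a pre-video survey had been given and gone undocumented, the point would be different and more serious, but nothing in either document suggests one.
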